## **8.2 Discontinuation of Study Treatment for an Individual Subject**

Study treatment will be discontinued if any of the following CTCAE categories are observed:

- Any related Grade 3 TEAE
- Any Grade 4 or higher TEAE

Additionally, subjects will be evaluated for possible discontinuation if the following changes in liver-related laboratory parameters are observed:

- Elevation of ALT > 2x above subject-specific baseline value (calculated using the median of the Screening and Day 1 value) and total bilirubin > 2x ULN:
  - ALT, AST, and total bilirubin must be re-tested within 72 hours.
  - Subjects with persistent elevations above the defined thresholds should be evaluated for discontinuation of study drug(s), independent of whether they are symptomatic or not.
- Elevation of only ALT > 2x above subject-specific baseline:
  - ALT, AST, and total bilirubin must be re-tested within 72 hours.

- Subjects with persistent elevations above the defined thresholds who are *symptomatic* should be evaluated for discontinuation of study drug(s).
- Subjects with persistent elevations above the defined thresholds who are *asymptomatic* may continue treatment under protocol-defined close observation criteria.
- Subjects continuing treatment under *close observation* should implement study procedures and assessments as part of the study conduct:
  1. Repeat liver enzyme and serum bilirubin tests two or three times weekly. The frequency of retesting can decrease to once a week or less if abnormalities stabilize or the trial drug has been discontinued and the subject is asymptomatic.
  2. Repeat additional tests to evaluate liver synthetic function (e.g., INR, direct bilirubin) as appropriate.
  3. Obtain a detailed history of symptoms and prior or concurrent diseases.
  4. Obtain a history of concomitant drug use (including nonprescription medications and herbal and dietary supplement preparations), alcohol use, recreational drug use, environmental toxin exposure, and special diets.
  5. Rule out acute viral hepatitis and other acute or chronic hepatobiliary diseases.

For the double-blind cohort, dose reductions will be allowed on a case by case basis for subjects receiving 6 mg or matched 6 mg placebo for safety or tolerability, but must be approved by the Medical Monitor. If approved, the subject will be decreased to 3 mg or the matched 3 mg placebo to be aligned with whether they were initially receiving active drug or placebo prior to the dose reduction. Subjects receiving 3 mg or matched 3 mg placebo will not be allowed to dose-reduce during the study period.

For the open-label single-blind cohort, no dose reductions will be allowed.

For the placebo-controlled 24-week histology cohort **no dose reductions** will be allowed. Additionally, ALT, AST, and all lipid laboratory results are blinded starting with Week 2 onward. The Medical Monitor will be reviewing and monitoring all laboratory results and if any of the liver related testing parameters are observed, investigators will be notified immediately to discuss further evaluation.

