## **7.1 Study-Stop Criteria**

The entire study or a single dosing arm may be discontinued or not initiated at the discretion of the Sponsor based on the occurrence of the following:

- AEs with respect to their nature, frequency, severity, and/or duration
- Medical or ethical reasons affecting the continued performance of the study
- Difficulties in the recruitment of patients
- Cancellation of drug development

The entire study will be discontinued by the sponsor if there are three or more related Grade 3 or Grade 4 treatment-emergent adverse events (TEAEs) of the same Common Terminology Criteria for Adverse Events (CTCAE) category.

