5. Other therapies for NAFLD or NASH: requires a stable regimen for at least 3 months prior to the Screening biopsy of record and throughout the study. May include vitamin E, milk thistle, thiazolidinediones and pentoxifylline.

Double-Blind Cohort:

Includes statins.

Open-Label Single Blind and Placebo Controlled 24 Week Histology Cohorts:

Includes statins if the conditions below are met. Other therapies may include vitamin E ( $> 800$  IU Placebo cohort only), milk thistle, thiazolidinediones (open-label, single-blind only) or pentoxifylline.

- a. Patient can be defined as statin naïve or experienced at Screening based on the following definitions:
  - i. **Statin-naïve:** no administration of statins within 3 months prior to enrollment.
  - ii. **Statin experienced:** administration of  $\leq 50\%$  of the maximal dose of current statin therapy.
- b. Requires a stable regimen for at least 3 months prior to Screening through Week 2.

The following are the acceptable daily doses of approved statin therapies, including combination preparations of statins and other lipid lowering agents. Also listed under Concomitant Medications in [Section 9.7](#).

- Atorvastatin:  $\leq 40$  mg/d
- Fluvastatin:  $\leq 40$  mg/d
- Lovastatin:  $\leq 40$  mg/d (immediate release),  $\leq 30$  mg/d (extended release)
- Pitavastatin:  $\leq 2$  mg/d
- Pravastatin:  $\leq 40$  mg/d
- Rosuvastatin:  $< 20$  mg/d (Note: must be  $<$  not  $\leq$  20 mg/d)
- Simvastatin:  $\leq 40$  mg/d

6. The following liver enzyme parameters must be met at Screening:
  - a. ALT and AST  $\leq 250$  IU/L
  - b. Abnormal ALT defined as:  $\geq 30$  IU in males and  $\geq 19$  IU in females
  - d. AST  $\geq 30$  IU/L except for patients with a historical biopsy within 3 months of screening with NAS of at least 4 with 1 point in each component and fibrosis stage 2 or 3 (Placebo-Controlled Cohort only)
7. The following additional laboratory parameters must also be met at Screening:

- a. Total bilirubin must be within normal range. For patients diagnosed with Gibert's Syndrome, please contact medical monitor/designee
  - b. INR  $\leq$  1.3 (in the absence of warfarin or other anticoagulant therapy)
  - c. Creatinine clearance  $\geq$  90 mL/min as calculated by Cockcroft-Gault equation
  - d. Alpha fetoprotein (AFP)  $<$  100 ng/mL
  - e. LDL C  $\leq$  185 mg/dL (except Double-blind cohort and  $\leq$  165 mg/dL for the Open-Label Single Blind )

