Prior participation in a clinical trial of NGM282 is excluded.

Open Label Single Blind and Placebo Controlled 24 Week Histology Cohorts:

Prior participation in a clinical trial of NGM282 is excluded **unless** previously enrolled into a placebo arm of the trial.

17. Patient with severe allergic or anaphylactic reactions to recombinant therapeutic proteins, fusion proteins, or chimeric, human, or humanized antibodies.
18. Participation in a study of another investigational agent within 28 days or five half-lives of the drug (whichever is longer) prior to Screening

19. Any acute or chronic condition that, in the opinion of the Investigator, would limit the patient's ability to complete and/or participate in this clinical study.
20. Pregnancy or lactation
21. Use of ezetimibe, colesevelam, cholestyramine, niacin, PCSK9 inhibitors, or other lipid-lowering agents within 3 months of Screening (except Double-blind cohort).

Placebo-Controlled 24 Week Histology Cohort Only

Use of any other lipid lowering agents or combination preparation of statins **except** ezetimibe when approved by MM/designee as second line lipid management therapy, within 3 months of Screening and throughout study

- a. colesevelam, cholestyramine, niacin, PCSK9 inhibitors (evolocumab or alirocumab), colestid, fibrates, fenofibrates, pharmacologic/prescribed fish oil

22. History or presence of ALT elevations or significant side effects indicative of statin intolerance (except Double-blind cohort).
23. Use of weight loss medications including: orlistat, phentermine, topiramate, qsymia, lorcaserin hydrochloride, naltrexone hydrochloride, liraglutide (use is for weight loss not T2D, e.g. Saxenda®), benzphetamine, diethylpropion and phendimetrazine, within 3 months of screening and throughout study

Additionally for all cohorts, the Investigator has discretion to repeat assessments if he/she believes there is a good chance the results were spurious and do not accurately represent the patient's true values. Repeat assessments must be conducted within the Screening Period.

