d A liver biopsy result is required at Screening and at Week 24. A historical biopsy within 3 months of Screening may be used instead of undergoing a new procedure. Week 24 biopsy should be obtained before the last dose of NGM282 or placebo with a visit window of -7 days and +3 days

e Lab results for ALT, AST, Total Cholesterol, LDL, HDL and triglycerides are blinded to site from Week 2 onward. Patient reports to clinic fasted on Day 1 or is rescheduled. All other clinic visits, chemistries and lipid panel will need to be retested if not fasted.

f A serum pregnancy test will be performed on all female subjects of child bearing potential at Screening, Week 24, and Week 30. A urine pregnancy test will be performed on all female subjects of child bearing potential at Day 1 (pre-dose).

g PK blood samples will be collected in all subjects before dosing themselves in the clinic (pre-dose) and at 2 hours (±20 mins) post-dose at Day 1, Week 12, and Week 24.

h Rosuvastatin will be dispensed at Weeks 2, 4, 8, 12 and 18 visits and subjects will be provided further dosing instruction based on their LDL-C levels and whether they are statin-naïve versus statin experienced. Subjects on a statin at screening will be dispensed additional rosuvastatin at Week 24 and continue through Week 30.

i Compliance with Rosuvastatin will be assessed at Week 30 for statin-experienced subjects only

j Baseline ALT reported result calculated using the median of the Screening and Day 1 value

k Adverse events will be monitored and recorded from patient signing informed consent through follow-up.

l Subjects will be instructed to self-inject NGM282 or placebo as close to the same time as possible each day in the abdomen and administer the next dose the following morning. Subjects will not self-inject NGM282 at home on clinic visit days.

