### **9.6.8 Week 18 Procedures**

Subjects will report to clinic fasted and not dosed with NGM282. The following procedures will be performed:

Pre-dose:

- Conduct physical examination.
- Measure vital signs (including temperature, respiratory rate, and seated blood pressure and pulse).
- Record concomitant medications.
- Record new and/or changes to AEs.
- Obtain blood for 10-hour fasted clinical laboratory samples (if not fasted chemistries and lipid panel will need to be retested)
  - Results are blinded for ALT, AST, Total Cholesterol, LDL, HDL and triglycerides

In-clinic dosing and dispensing:

- Collect old NGM282 study-drug kit/diary and conduct reconciliation.
- Collect old rosuvastatin medication bottle/diary and conduct reconciliation.
- If subject is taking statins, evaluate tolerability and continue therapy to Week 24 for statin naïve or Week 30 for statin experienced
- Dispense new NGM282 study-drug kits (5) and diary.
- Dispense new rosuvastatin medication/diary.
- Oversee subject's NGM282 study-drug self-administration (from new kit).
- Perform LISSA evaluation.

Before clinic discharge:

- Remind subject to bring study drug kits/diary and to not self-inject NGM282 at home on clinic visit days.
- Schedule Week 24 (End of Treatment) visit and remind subject for home dosing to administer NGM282 or placebo as close as possible to the same time each day

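### 24-week cohort: with ALT and AST hidden from sites, the written duty to notify has no AST trigger, and at high baselines its ALT trigger can come after Grade 3

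*Protocol*

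**What the plan says.** Protocol Table 4, footnote e, for the 24-week cohort: "Lab results for ALT, AST, Total Cholesterol, LDL, HDL and triglycerides are blinded to site from Week 2 onward". Sections 8.2 and 9.9.4 say the same and give the monitoring of these results to the sponsor's Medical Monitor or designee. Total bilirubin is not on the withheld list.

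Section 8.2 then states the duty to pass a result on: "if any of the liver related testing parameters are observed, investigators will be notified immediately to discuss further evaluation". The liver-related parameters listed in that section are two:

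- ALT above twice the subject-specific baseline (median of the Screening and Day 1 values) together with total bilirubin above twice the ULN;
- ALT alone: "Elevation of only ALT > 2x above subject-specific baseline".

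AST appears there only as a test to repeat within 72 hours after an ALT trigger.

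The same section contains a mandatory rule: "Study treatment will be discontinued if any of the following CTCAE categories are observed". The categories are a related Grade 3 event and any event of Grade 4 or higher. Section 7.1 adds: "The entire study will be discontinued by the sponsor if there are three or more related Grade 3 or Grade 4 treatment-emergent adverse events", within one CTCAE category. Under Sections 11.1 and 11.2 the investigator grades severity by CTCAE v4.03 and decides relatedness.

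On entry, Section 8.1.1, criterion 6, begins "The following liver enzyme parameters must be met at Screening" and allows ALT and AST up to 250 IU/L.

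**The concern.** The stopping rule for an individual subject works on CTCAE grade and relatedness, and both are the investigator's decisions. In this cohort the investigator cannot see the two enzymes that would show hepatocellular injury. The notification sentence is meant to bridge that blind, but it is tied to a multiple of baseline ALT and not to grade, and it leaves AST out. If the sentence is followed exactly and no further, the person who must grade and attribute the event need not be told of a Grade 3 AST result, or of a Grade 3 ALT result in a subject who entered high.

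The expected effect of NGM282 on ALT is a fall (Section 5.1.3 reports decreases in the type 2 diabetes study). The stake is therefore unexpected liver injury, in subjects who may also be taking rosuvastatin 20 or 40 mg.

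**Working it through.** The plan states no figure to reproduce; this is a comparison of thresholds.

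**Inputs from the documents.** Notice is due when ALT exceeds 2B, where B is baseline ALT (Section 8.2). ALT and AST may be up to 250 IU/L at Screening (Section 8.1.1).

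**Assumed input.** Grade 3 ALT starts above C. The protocol names CTCAE v4.03 but prints neither the cut-off nor the laboratory ULN. I take C = 150 to 300 IU/L, which is 5 × ULN for a ULN of 30 to 60.

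**Step 1, AST.** Both listed parameters require ALT above 2B. An AST rise of any size, with ALT at or below 2B, meets neither. Results are withheld at eight visits: Weeks 2, 4, 6, 8, 12, 18, 24 and 30. The last dose is taken at Week 24, and Week 30 is six weeks later, so a treatment stop can still have effect at 8 − 2 = 6 visits. An AST trigger exists at 0 of these 6. This step needs no assumption.

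**Step 2, ALT.** Grade 3 without notice due is the range from C to 2B. It exists when 2B > C, that is, when B > C/2. For subjects not already above C at entry and within 250 IU/L:

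| Assumed C (IU/L) | Gap opens at B above C/2 | Baselines affected |
|---|---|---|
| 150 | 75 | above 75, to 150 |
| 200 | 100 | above 100, to 200 |
| 250 | 125 | above 125, to 250 |
| 300 | 150 | above 150, to 250 |

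**Step 3, examples.** With B = 125 and C = 200, notice is due above 2 × 125 = 250, so ALT of 201 to 250 is Grade 3 with no notice due. With B = 150 and C = 200, Grade 3 starts above 200 and notice is due above 300. With B = 60, notice is due above 120, below every C in the table, so there is no ALT gap and the baseline rule is the stricter one.

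**Step 4, sensitivity.** With B at most 250, 2B is at most 500, so the ALT gap disappears only if C is 500 IU/L or more. If the trigger is read as a rise of twice baseline on top of baseline (3B), the gap is wider: it opens at C/3, which is 50 to 100 IU/L over the assumed range.

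**The case against.** The strongest reply is that the Medical Monitor sees everything. A reader might infer that a Grade 3 AST result would go unseen, or would bypass the stopping rules. The documents do not support that. Section 8.2 commits the Medical Monitor to review all results, and nothing bars passing one on. Section 11.1 records adverse events however they are identified. The 8.2 stop does not say who must observe the event, and the 7.1 stop is carried out by the sponsor. This stands: the gap is in what must be communicated, not in what is reviewed. It does not close the point, because grading and attribution remain with the investigator and notice outside the two ALT parameters is discretionary.

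It can be said that the notification wording is loose enough to include AST. On that reading no AST threshold exists, so the sentence still needs one.

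A trigger relative to baseline is also a coherent choice where abnormal ALT is an entry requirement. Every ALT value in the gap is at most twice the subject's own baseline; 125 to 201 is a 1.6-fold rise. A bare grade trigger would also be noisy: with C = 200, a move from 195 to 201 (about 3%) counts as worsening to Grade 3. This stands, and the fix must allow for it.

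Three further inferences should not be drawn.

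- **Laboratory tables.** A reader might conclude that the SAP never counts Grade 3 laboratory results by arm. SAP 9.3 describes low/normal/high shift tables, and the Grade 3 or higher table in SAP 9.2 counts adverse events. But the index of tables is redacted and the mock-ups are a separate document, so the conclusion cannot be reached.
- **Lipids.** A similar gap might be inferred for the withheld lipids. The Section 10.4 algorithm figures are not in the available text, and Section 10.4.2 gives the Medical Monitor discretion without a week limit.
- **Statin tolerability.** At Week 18 the instruction is "If subject is taking statins, evaluate tolerability and continue therapy to Week 24" (statin naïve), and exclusion 22 refers to "History or presence of ALT elevations or significant side effects indicative of statin intolerance". That exclusion is an entry criterion, and a change to ezetimibe needs approval from the Medical Monitor, who sees ALT. The text does not establish a defect.

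**Conclusion.** The point holds as a gap in the written duty to notify, and the sponsor should close it. The AST part follows from the text alone: no AST trigger at any of the six visits where stopping could still matter. The ALT part rests on an assumed Grade 3 cut-off of 150 to 300 IU/L, under which subjects with baseline ALT above 75 to 150 IU/L can reach Grade 3 before notice is due; it would vanish only at a cut-off of 500 IU/L or more. The documents do not say how many subjects enter in that range, so the practical size is unknown. The Medical Monitor's review is a real safeguard, but notice beyond the two ALT parameters is left to discretion, while the treatment stop for a related Grade 3 or any Grade 4 or higher event depends on an investigator who need not be told.

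**What to change.** Extend the notification sentence in Section 8.2 so that, in addition to the two existing parameters, investigators are notified immediately, and ALT, AST and total bilirubin are retested within 72 hours, if:

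- (a) AST exceeds twice the subject-specific baseline, defined as for ALT (median of Screening and Day 1), and is above the ULN; or
- (b) ALT or AST has worsened from baseline to CTCAE Grade 3 or higher. The result is confirmed on retest before it is treated as a Grade 3 TEAE, and the investigator judges clinical relevance and relatedness.

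The ULN floor in (a) is needed because criterion 6 waives the AST minimum of 30 IU/L in this cohort for patients with a qualifying biopsy within 3 months. A subject entering at 18, for example, would otherwise trigger an alert above 36. In (b), the worsening condition avoids alerts for subjects who enter high and stay stable; confirmation and the investigator's judgement deal with small moves across the cut-off.

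The cost is two clauses in one sentence, a few extra alerts and retests, possibly some extra treatment stops that Section 8.2 already intends, and a slight risk that an alert hints at the treatment arm. No change to the lipid or statin procedures or to the SAP is asked for here.

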### 8.3 Discontinuation of Subjects from Study Participation

Subjects will be informed that they are free to withdraw from the study at any time and for any reason. The Principal Investigator (PI) may remove a subject from the study if, in the PI's opinion, it is not in the best interest of the subject to continue the study. Subjects may be discontinued due to a change in compliance with an inclusion/exclusion criterion that is clinically relevant and affects subject safety, occurrence of AEs, occurrence of pregnancy, or

administration of non-permitted concomitant medication that might affect subject safety or study assessments/objectives. Notification of discontinuation will be made immediately to the Sponsor's Medical Monitor. In case of premature discontinuation of study participation, efforts will be made to perform all final EOT and EOS visits/assessments. The date the subject is withdrawn from the study and the reason for discontinuation will be recorded on the subject's Case Report Form (CRF). All withdrawn subjects will be followed until resolution of any AEs or until any unresolved AEs are judged by the PI to have stabilized.

## **9                   Study Methods**

### **9.1                  Schedule of Study Procedures for Double-blind Cohort**

The Schedule of Study Procedures for the double-blind cohort is shown in [Table 2](#). The visits should occur as close to the intended dates as possible. However, there is an acceptable  $\pm 3$  day window for individual scheduled visits. Subjects attending any visits out of windows from Day 1 to Week 12/Early Withdrawal (EOT) visit should be brought back into compliance with the overall study-visit schedule as soon as possible thereafter. Subjects will then return to the clinic at Week 16 (or 4 weeks after last dose) for an EOS follow-up visit.

The Investigator has discretion to repeat assessments if he/she believes the results do not accurately represent the patient's true values. Repeat assessments must be conducted within the 4-week ( $\pm 5$  days) Screening Period.

**Table 2. Schedule of Study Procedures for Double-Blind Cohort**

Study Procedure	Days -28 to -1 (Screening) a	Day 1	Wk 1	Wk 2	Wk 4	Wk 8	Wk 12 (EOT)/ EW	Wk 16 (EOS)
Informed consent	X							
Demographics	X							
Medical history	X							
Inclusion/exclusion criteria	X	X						
Height	X							
Body weight, BMI, waist circumference	X	X					X	X
Physical exam	X	X		X	X	X	X	X
12-lead ECG	X	X		X			X	X
Vital signs	X	X	X	X	X	X	X	X
Liver biopsy b (or tissue slides)	X							
MRI c	X						X	
Prior and concomitant medications	X	X	X	X	X	X	X	X
Randomization		X						
Study drug self-administration training		X	X	X	X			
Dispense study drug		X	X	X	X	X		
Medication compliance			X	X	X	X	X	
Adverse event (AE) evaluations		X	X	X	X	X	X	X
LISSA evaluations d		X	X	X	X	X	X	X
PK blood samples e		X	X	X	X	X	X	X
Chemistry [fasted $\geq$ 10 hours]	X	X	X	X	X	X	X	X
Complete blood count (CBC)	X	X	X	X	X	X	X	X
Urinalysis (UA)	X	X			X		X	X
Fasting lipid panel		X			X		X	
Lipoprotein particles		X					X	
██████████		████					████	
HbA1c	X	X					X	
Insulin level and HOMA-IR	X	X					X	
Stool sample		X					X	
Hepatitis and HIV screen	X							
Urine drug screen	X							

**Table 2. Schedule of Study Procedures for Double-Blind Cohort (cont'd)**

Study Procedure	Days -28 to -1 (Screening) a	Day 1	Wk 1	Wk 2	Wk 4	Wk 8	Wk 12 (EOT)/EW	Wk 16 (EOS)
Pregnancy test f	X	X					X	X
C4 and serum bile acids		X					X	
Alpha fetoprotein	X							
Vitamin D		X					X	X
International Normalized Ratio	X	X					X	X
[REDACTED]		[REDACTED]			[REDACTED]		[REDACTED]	[REDACTED]
Cytokines (IL-6, TGF- $\beta$ )		X			X		X	
[REDACTED]		[REDACTED]					[REDACTED]	
Anti-drug antibodies		X		X	X	X	X	X
Neutralizing antibodies		X		X	X	X	X	X
Exploratory biomarkers		X					X	

AE = adverse event; BMI = body mass index; C4 = 7-alpha-hydroxy-4-cholesten-3-one; CBC = complete blood count; ECG = electrocardiogram; EOS = End of Study; EOT = End of Treatment; EW = Early Withdrawal; [REDACTED] HIV = human immunodeficiency virus; HOMA-IR = homeostasis model assessment-estimated insulin resistance; [REDACTED]; IL-6 = interleukin 6; LISSA = local injection-site symptom assessment; [REDACTED]; MRI = magnetic resonance imaging; MRI-PDFF = magnetic resonance imaging–proton density fat fraction; PK = pharmacokinetic; TGF- $\beta$  = transforming growth factor beta; UA = urinalysis; Wk = week.

a There must be a minimum of 14 days between Screening and Day 1 visits for adequate separation of the repeated Chemistry (liver function tests) and International Normalized Ratio assessments.

b Liver biopsy will be performed only in patients who do not have a biopsy available within 6 months of Screening.

c Screening MRI-PDFF result will serve as Baseline for efficacy endpoint analysis. Adiposity assessments will be collected as part of the standard MRI procedure at all sites. [REDACTED]

d LISSA evaluations will be performed pre- and post-dose for all on-treatment visits. At Week 16, a single LISSA will be performed to assess prior-dose injection-site reactions.

e PK blood samples will be collected before subjects dose themselves in the clinic (pre-dose). At Day 1 and Week 12, an additional PK blood sample will be collected 2 hours post-dose.

f A serum pregnancy test will be performed on all female subjects at Screening, Week 12, and Week 16. A urine pregnancy test will be performed on all female subjects at Day 1 (pre-dose).

